## PROGRAMMING:

- 1) Ask all respondents
- 2) Randomize rows
- 3) Free text field for the "Other" response option is a force response

Abbreviated Protocol: 20210065

Date: 22 March 2021 Page 24 of 37

19. Prior to today, were you aware of the **BLINCYTO REMS Letter or email for Healthcare Providers?** 

(Select one answer)

a. Yes
b. No
c. I am not sure

#### PROGRAMMING:

- 1) Ask all respondents
- 2) Example BLINCYTO REMS Letter or Email for Healthcare Providers visual aid to be displayed on screen
- 3) If "Yes," proceed to Question 20; if "No" or "I am not sure," skip to Question 22
- 20. Did you receive and/or do you have access to the **BLINCYTO REMS Letter or** email for Healthcare Providers?

(Select one answer)

a. Yes	
b. No	
c. I am not sure	

#### PROGRAMMING:

- 1) Ask if Q19 is "Yes"
- 2) Example BLINCYTO REMS Letter or Email for Healthcare Providers visual aid to be displayed on screen
- 3) If "Yes," proceed to Question 21; if "No" or "I am not sure," skip to Question 22
- 21. Which of the following best describes how much of the **BLINCYTO REMS Letter**or email for Healthcare Providers
  you had an opportunity to read?

(Select one answer)

a. All of it	
b. Most of it	
c. Some of it	
d. None of it	

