will also be calculated. Responses for questions related to preparation instructions and access to checklists and Product Information/Package Insert (PI) in the workplace setting and knowledge of indication for BLINCYTO will be described with proportions and 95% CIs for each response option. Similarly, proportions and 95% CIs will be reported for the awareness and use of the REMS materials (responses for Questions 15 to 32 in Appendix A).

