#### PROGRAMMING:

- 1) Ask if Question 22 is "Yes"
- 2) Example BLINCYTO REMS materials disseminated by Professional Societies visual aid to be provided on screen
- 3) If "Yes," proceed to Question 24; if "No" or "I am not sure," skip to Question 25 if PHARMACIST respondent OR skip to Question 28 if RN respondent
- 24. Which of the following best describes how much of the **BLINCYTO REMS Letter**or email for Professional Societies you had an opportunity to read?

a. All of it	
b. Most of it	
c. Some of it	
d. None of it	

Abbreviated Protocol: 20210065

Date: 22 March 2021 Page 26 of 37

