## **PROGRAMMING:**

- 1) Ask if Q25 is "Yes"
- 2) Example BLINCYTO REMS Letter or email for Hospital and Home Healthcare Pharmacists visual aid to be provided on screen
- 3) If "Yes," proceed to Question 27; if "No" or "I am not sure," skip to Question 28
- 27. Which of the following best describes how much of the **BLINCYTO REMS Letter**or email for Hospital and Home Healthcare Pharmacists you had an opportunity to read?

a. All of it	
b. Most of it	
c. Some of it	
d. None of it	

Abbreviated Protocol: 20210065

Date: 22 March 2021 Page 27 of 37

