#### PROGRAMMING:

- 3) Ask all respondents
- 4) Example Full Prescribing Information for BLINCYTO visual aid to be provided on screen
- 5) If "Yes," proceed to Question 32; if "No" or "I am not sure," skip to Question 33
- 32. Have you read the Full Prescribing Information for BLINCYTO?

(Select one answer)

a. Yes	
b. No	

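### Questions 21, 24, 27 and 30 do not distinguish having had the chance to read a REMS document from having read it, so readership may be overstated (minor)

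*Protocol*

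**What the plan says.** Appendix A handles each REMS document in three steps: awareness, then receipt or access, then amount read. The second step (Questions 20, 23, 26 and 29) opens with "Did you receive and/or do you have access to the" and names the document. Only those who answer Yes reach the third step.

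The third step uses the same phrase for all four documents:

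- Question 21, letter for healthcare providers: "you had an opportunity to read"
- Question 24, Professional Societies letter: "email for Professional Societies you had an opportunity to read"
- Question 27, pharmacist letter (pharmacists only): "email for Hospital and Home Healthcare Pharmacists you had an opportunity to read"
- Question 30, Fact Sheet: the same phrase as Question 21

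The options run from *All of it* through *Most of it* and *Some of it* to *None of it*. For the Prescribing Information, Question 32 asks directly: "Have you read the Full Prescribing Information for BLINCYTO".

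Section 3, Descriptive Analyses, states that "proportions and 95% CIs will be reported for the awareness and use of the REMS materials", and names Questions 15 to 32 as the source.

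**The concern.** Access is settled by the preceding question, so the third step is there to add how much was read. Its stem goes back to opportunity. A respondent who holds the letter and never opened it can truthfully answer *All of it* (nothing prevented reading) or *None of it* (it was not read). The same behaviour can fall at opposite ends of the scale, and no other item shows which sense the respondent had in mind.

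The letters and the Fact Sheet are components of the REMS communication plan (section 1), and how far they were read is part of a planned output. If some respondents answer on opportunity, the reported proportions will look better than actual reading. Nothing in the collected data would allow a correction afterwards.

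**Working it through.** **1. Direction of any error.** Having read a given amount implies having had the opportunity to read it; the reverse does not hold. An answer on opportunity is therefore never lower than an answer on reading. Any error from this source runs upward.

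**2. What else measures use.** Question 18, asked of all respondents, has separate Yes/No rows for the Fact Sheet and for REMS communications as sources of learning about preparation and administration errors. It does not ask how much was read. Questions 21, 24, 27 and 30 are the only items that do.

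**3. The plan's own precision figures.** Section 3, Sample Size, Table 1 gives 95% half-widths. With half-width = 1.96 × √(p(1-p)/n):

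- n = 100, p = 50%: 1.96 × √(0.25/100) = 0.098; Table 1 gives 0.098.
- n = 200, p = 50%: 1.96 × √(0.25/200) = 0.069; Table 1 gives 0.069.

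All ten cells reproduce to rounding.

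**4. Size of a possible overstatement.** Let p be the true share, among those who reach the item, who read all of the document. Let m be the share of the remainder who choose *All of it* because they answer on opportunity. Those who read everything choose *All of it* in either sense, so:

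reported = p + m(1-p), and overstatement = m(1-p).

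The documents give neither p nor m. For assumed values, the reported percentage (overstatement in points) is:

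| True p | m = 0 | m = 10% | m = 30% |
|---|---|---|---|
| 30% | 30 (0) | 37 (7) | 51 (21) |
| 50% | 50 (0) | 55 (5) | 65 (15) |
| 70% | 70 (0) | 73 (3) | 79 (9) |

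**5. Set against sampling error at p = 50%.** With n = 100, the overstatement exceeds the half-width of 9.8 points when m > 0.098/0.5, about 20%. Fewer than the full group will normally reach these items, because each sits behind two Yes answers. If 60 respondents of one type did so (an assumption), the half-width would be 1.96 × √(0.25/60) = 12.7 points and m would have to exceed 0.127/0.5, about 25%. The overstatement passes sampling error only in the upper part of the assumed range for m.

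**The case against.** The strongest reply is that respondents will take the phrase as how much they managed to read. They have just confirmed access, and a graded scale ending in *None of it* makes little sense as a measure of availability. This largely stands. A reader might infer that these items measure availability and that the estimate of use is inflated. The questionnaire does not support that: availability has its own question, the scale points towards reading, and no figure in the protocol shows inflation.

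Use is also not carried by these items alone. Question 16 (website access), Question 18 and Question 32 fall in the same reported set, and no single use score is defined. The main endpoint, in section 3, is scored from Questions 7 or 8, 10 and 11. All of this stands and limits the importance of the point.

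The contrast with Question 32 is weak as a comparability argument. That item is Yes/No, the four readership items are graded, and no comparison between them is planned. It shows only that direct wording was available.

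Section 3, Survey Pre-testing, checks that questions are understood and allows the instrument to be improved. That gives an occasion for the change but is a weak means of detecting the problem. A respondent who takes the phrase literally is not confused and has nothing to report. With about five nurses and five pharmacists, and two Yes answers needed to reach each item, few may see it.

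What remains is that the stem admits two truthful answers for the same behaviour, and the error, if any, goes one way.

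**Conclusion.** The point holds as a minor wording defect in secondary descriptive items. The four stems are ambiguous between opportunity and reading, and readership of the REMS letters and Fact Sheet may be overstated as a result. The size cannot be derived from the protocol and may be nil. At p = 50% and m between 10% and 30%, both assumed, it would be 5 to 15 points.

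One might also take the overstatement to equal m itself, that is 10 to 30 points. That counts respondents who read the whole document and would give the same answer in either sense; the right quantity is m(1-p).

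The knowledge endpoint and its 80% threshold are not affected.

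**What to change.** Before programming, reword the stems of Questions 21, 24, 27 and 30 to *How much of (name of document) have you read?* and keep the four response options. If the present phrase was meant to spare respondents embarrassment, a short neutral lead-in can do that while the stem asks about reading.

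The cost is four stems. Section 3, Study Design, mentions similar surveys at 18 months, 3 years and 5 years. Their wording is not shown, and this protocol plans no comparison with them. If they used the present phrase, a footnote to the results should record the change.

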## PROGRAMMING:

1) Ask if Q20 is "Yes"

Abbreviated Protocol: 20210065

Date: 22 March 2021 Page 25 of 37

2) Example BLINCYTO REMS Letter or Email for Healthcare Providers visual aid to be displayed on screen

22. Prior to today, were you aware of the BLINCYTO REMS materials through information disseminated by **Professional Societies**?

(Select one answer)

a. Yes	
b. No	
c. I am not sure	

#### PROGRAMMING:

- 1) Ask all
- 2) Example BLINCYTO REMS materials disseminated by Professional Societies visual aid to be provided on screen
- 3) If "Yes," proceed to Question 23; if "No" or "I am not sure," skip to Question 25
- 23. Did you receive and/or do you have access to the **BLINCYTO REMS Letter or** email for Professional Societies?

(Select one answer)

a. Yes
b. No
c. I am not sure

#### PROGRAMMING:

- 1) Ask if Question 22 is "Yes"
- 2) Example BLINCYTO REMS materials disseminated by Professional Societies visual aid to be provided on screen
- 3) If "Yes," proceed to Question 24; if "No" or "I am not sure," skip to Question 25 if PHARMACIST respondent OR skip to Question 28 if RN respondent
- 24. Which of the following best describes how much of the **BLINCYTO REMS Letter**or email for Professional Societies you had an opportunity to read?

a. All of it	
b. Most of it	
c. Some of it	
d. None of it	

Abbreviated Protocol: 20210065

Date: 22 March 2021 Page 26 of 37

#### PROGRAMMING:

1) Ask if Question 23 is "Yes"

- 2) Example BLINCYTO REMS materials disseminated by Professional Societies visual aid to be provided on screen
- 25. Prior to today, were you aware of the **BLINCYTO REMS Letter or email for Hospital and Home Healthcare Pharmacists?**

(Select one answer)

a. Yes	
b. No	
c. I am not sure	

#### PROGRAMMING:

- 1) Ask all PHARMACIST respondents
- 2) Example BLINCYTO REMS Letter or email for Hospital and Home Healthcare Pharmacists visual aid to be provided on screen
- 3) If "Yes," proceed to Question 26; if "No" or "I am not sure," skip to Question 28
- 26. Did you receive and/or do you have access to the **BLINCYTO REMS Letter or**email for Hospital and Home Healthcare Pharmacists?

(Select one answer)

a. Yes
b. No
c. I am not sure

## **PROGRAMMING:**

- 1) Ask if Q25 is "Yes"
- 2) Example BLINCYTO REMS Letter or email for Hospital and Home Healthcare Pharmacists visual aid to be provided on screen
- 3) If "Yes," proceed to Question 27; if "No" or "I am not sure," skip to Question 28
- 27. Which of the following best describes how much of the **BLINCYTO REMS Letter**or email for Hospital and Home Healthcare Pharmacists you had an opportunity to read?

a. All of it	
b. Most of it	
c. Some of it	
d. None of it	

Abbreviated Protocol: 20210065

Date: 22 March 2021 Page 27 of 37

#### PROGRAMMING:

- 1) Ask if Q26 is "Yes"
- 2) Example BLINCYTO REMS Letter or email for Hospital and Home Healthcare Pharmacists visual aid to be provided on screen
- 28. Prior to today, were you aware of the **BLINCYTO REMS Fact Sheet**?

(Select one answer)

a. Yes	
b. No	
c. Lam not sure	

#### **PROGRAMMING:**

- 1) Ask all respondents
- 2) Example BLINCYTO REMS Fact Sheet visual aid to be provided on screen
- 3) If "Yes," proceed to Question 29; if "No" or "I am not sure," skip to Question 31
- 29. Did you receive and/or do you have access to the **BLINCYTO REMS Fact**

## Sheet?

(Select one answer)

a. Yes	
b. No	
c. I am not sure	

#### PROGRAMMING:

- 1) Ask if Question 28 is "Yes"
- 2) Example BLINCYTO REMS Fact Sheet visual aid to be provided on screen
- 3) If "Yes," proceed to Question 30; if "No" or "I am not sure," skip to Question 31
- 30. Which of the following best describes how much of the **BLINCYTO REMS Fact Sheet** you had an opportunity to read?

a. All of it
b. Most of it
c. Some of it
d. None of it

Abbreviated Protocol: 20210065

Date: 22 March 2021 Page 28 of 37

#### PROGRAMMING:

- 1) Ask if Question 29 is "Yes"
- 2) Example BLINCYTO REMS Fact Sheet visual aid to be provided on screen
- 31. Did you receive and/or do you have access to the Full Prescribing Information for BLINCYTO?

(Select one answer)

a. Yes	
b. No	
c I am not sure	

#### PROGRAMMING:

- 3) Ask all respondents
- 4) Example Full Prescribing Information for BLINCYTO visual aid to be provided on screen
- 5) If "Yes," proceed to Question 32; if "No" or "I am not sure," skip to Question 33
- 32. Have you read the Full Prescribing Information for BLINCYTO?

(Select one answer)

a. Yes	
b. No	

#### PROGRAMMING:

- 1) Ask if Question 31 is "Yes"
- 2) Example Full Prescribing Information for BLINCYTO visual aid to be provided on screen

## **Demographic Questions**

35. How long have you worked as a healthcare provider (starting with the completion of your postgraduate training, if applicable)?

- a. Less than 1 year
- b. 1 to 5 years
- c. 6 to 10 years
- d. More than 10 years

Abbreviated Protocol: 20210065

Date: 22 March 2021 Page 29 of 37

## PROGRAMMING:

1) Ask all respondents

Abbreviated Protocol: 20210065

Date: 22 March 2021 Page 30 of 37

## Appendix C. Amgen Safety Reporting Form

Project ID: 20		Observational Research				Date of Reporter Awareness:				
		Α	Safety Re	Form	Date Reported to Amgen:					
		Amgen S [name] or	afety Fax : [name]	email: [contact]						
1. Initial:	F	ollow-up:	]							
2. Site Number			ct Number:							
3. Indicate (PC)	event type	: (Please tick	all that apply)		Safety Findi  Device Effect	· –	Product Complaint			
		ndor/Investi		5.	Reporter ID					
Name	Phone	F	ax	Name or ID		Phone	Fax			
Address				Address						
City	State/Pro	vince		City		State/Prov	vince			
Postal Code	Country			Postal Code	!	Country				
6. HCP Co	ntact Detail	s (if other th	an reporter)	7.	Patient					
Name				Initials (optional)	Sex	Age (at time of event)	Was consent obtained to follow-up with HCP?			
Country				, ,	□ F □	,	, ☐ Yes			
Address					M		□ No			
City	State	/Province	Postal Code	Weight	Height	Race	Is patient also			
Phone	F	ax			□in		reporter?			
				lbs	☐ cm		□No			
8. Medical	History (in	clude	9. Suspe	kg ct Produc	t Information	include d	osing details)			
	diagnosis)	Siddo	0. Guopa	000110000		· (iiioiaao a	oonig dotailo/			
			Product/Device:							
			Indication:							
			Start Date day month year		top Date month year	Dose	Route Frequency			
			D (III 10 : -				\ \n' \cdot \n' \n' \cdot \n' \cdot \n' \cdot \n' \cdot \n' \cdot \n' \cdot \n' \n' \cdot \n' \cdot \n' \cdot \n' \cdot \n' \cdot \n' \cdot \n' \n' \cdot \n' \cdot \n' \cdot \n' \cdot \n' \cdot \n' \cdot \n' \n' \cdot \n' \cdot \n' \cdot \n' \cdot \n' \cdot \n' \cdot \n' \n' \cdot \n' \cdot \n' \cdot \n' \cdot \n' \cdot \n' \cdot \n' \n' \cdot \n' \cdot \n' \cdot \n' \cdot \n' \cdot \n' \cdot \n' \n' \n' \cdot \n' \cdot \n' \cdot \n' \cdot \n' \cdot \n' \cdot \n'			
Pregnant? ☐ Yes Yes ☐ No	□ No L	actating?	Prefilled Syringe?  ☐ No	∐ Yes	Lot #	n	Vial Size			
Allergy: Other Device					Serial #	dele / Heden eco				
Allergy:			——————————————————————————————————————		Unavaila	able / Unknow	n			
10. AF Oth	er Safety Ei	nding, or PC	ADE information	1			HCP ONLY			
Finding (List main event first; one event per line)	Ornest (I	Resolved Date f patient died,	Hospitalization ospitalized? ☐ Yes ☐ o rolonged ospitalization? ☐ Yes ☐	Serious ( 01 Fatal 02 Immedialife-threate	ately ning 1=none 2=dose reduced lization 3=dose		e Severit Relationship y 1 mild 2=moder ce			

Abbreviated Protocol: 20210065

Date: 22 March 2021 Page 32 of 37

			(provide autopsy repo	ort)   -	Admitting dx  Date Admitte  Discharged	d Date	disability /incapacity 05 Congenital anomaly/birth defect 06 Other significant medical hazard 07 Non serious	4=drug withdrawn 5=drug rechallenge (state outcome)	03 Not recovered/n ot resolved 04 Recovered/ resolved with sequelae 05 Fatal		have b	ent may een I by the ct/Device
		day month year	day month y	ear	day month year	day month year			06 Unknown		Produ	ct Device
		,,,,,,,,,,,,,,,,,,,,,,,,,,,,,,,,,,,,,,,			7	7+					ΥN	I Y
											V N	. N
											ΥN	N
											ΥN	1 N
											ΥN	- z ≺
											ΥN	ΙY
11. (	Conco	mitant Me	dications (	ea. c	chemoth	erapy)						' N
Medication N		Start Date	Stop Date		suspect	Continuin	g Dose	Route	Frequer	ıcy Tr	eatmen	t Meds
		Day Month	Day Month	No	Yes	No						
		Year	Year			Yes						
12. F	Releva	nt Labora	tory Value	s (in	clude da	tes, allerg	ies, and any re	elevant pric	or therapy	)		
Date	Test											
Day Month	Unit											
Year												
13. (	Other I	Relevant T	est (diagn	ostic	cs and pr	ocedures	5)					
	Date			Add	ditional T	ests	Resu	Its		Units		
Day	Month \	Y ear										
14. [	)escri	ption: Prov	vide chrono	logic	cal summa	ary and de	tails of AE sym	ptoms, PC	or ADE tha	at are l	isted i	n
							ns including those ເ					

Abbreviated Protocol: 20210065

Date: 22 March 2021 Page 33 of 37

## Appendix D. Additional Safety Reporting Information

Adverse Event Severity Scoring System

Grade	Amgen Standard Adverse Event Severity Scoring System
1	MILD: Aware of sign or symptom, but easily tolerated
2	MODERATE: Discomfort enough to cause interference with usual activity
3	SEVERE: Incapacitating with inability to work or do usual activity

CONFIDENTIAL

Abbreviated Protocol: 20210065

Date: 22 March 2021 Page 34 of 37

## Appendix E. Pregnancy and Lactation Notification Forms

## **Pregnancy Notification Form**

Report to Amgen at: USTO [contact], Non-US [contact] or email (worldwide): [contact]

I. Gase Au	IIIIIISuauve IIII	omation			
☐ Study Design	: Interventional Retrospective)	☑ Observationa		onal ☑ Prospective	
2. Contact	Information				
Investigator N	lame			Site #	
Phone ()	Fax (	)		Email	
Institution					
Address					
3. Subject Information					
Subject ID #	Subject Gend	der:	∐ Male S u	ibject age (at onset): (in	years)
4. Amgen Product Exposu	ure				
Amgen Product	Dose at time of conception	Frequency	Route	Start Date	
BUNOVTO (UE (CONT.)	conception				
BLINCYTO (blinatumomab)				mm/dd/yyy	/y
Was the Amgen product (or study drug) discontinued?					
5. Pregnancy Information					
Pregnant female's last menstrual		m/ dd	/ yyyy	Unknown	□ N/A
Estimated date of delivery mm/ dd/ yyyy  If N/A, date of termination (actual or planned) mm/ dd/ yyyy					
Has the pregnant female already delivered?					
If yes, provide date of delivery: mm/ dd/ yyyy					
Was the infant healthy? ☐ Yes ☐ No ☐ Unknown ☐ N/A					
If any Adverse Event was experienced by the infant, provide brief details:					
Form Completed by:					
Print Name: Title:					
				Amgen Proprietary - For Internal	Use Only
CONFIDENTI	ΔΙ			AMO	EN®

Signature:	Date:

## **AMGEN**® Lactation Notification Form

Report to Amgen at: USTO [contact], Non-US [contact] or email (worldwide): [contact]

1. Case Administrative Information				
Protocol/Study Number: Amgen Protocol Number: 20210065				
Study Design: Interventional				
0. 0				
2. Contact Information Investigator Name				Site #
Phone ()	Fax (	)		Email
Institution				
Address				
3. Subject Information				
Subject ID #	Subject age (	at onset): (in ye	ars)	
4. Amgen Product Exposu	ire			
Amgen Product	Dose at time of breast feeding	Frequency	Route	Start Date
BLINCYTO (blinatumomab)				mm/dd/yyyy
Was the Amgen product (or study drug) discontinued? ☐ Yes ☐ No  If yes, provide product (or study drug) stop date: mm/dd/yyyy  Did the subject withdraw from the study? ☐ Yes ☐ No				
5. Breast Feeding Informa	tion			
Did the mother breastfeed or provide	de the infant with pur	nped breast milk whi	le actively tal	king an Amgen product? ☐ Yes ☐ No
If No, provide stop date: m	ım/dd	/yyyy		
Infant date of birth: mm/d	ld/yyyy			
Infant gender: ☐ Female ☐ Male				
Is the infant healthy? ☐ Yes ☐ No ☐ Unknown ☐ N/A				
If any Adverse Event was experienced by the mother or the infant, provide brief details:				
Form Completed by:				
Print Name: Title:				
				Answer Description - For Interest U.S. Och

Abbreviated Protocol: 20210065

Date: 22 March 2021 Page 37 of 37

